7.4 Assessment of Safety

Safety of Forielle will be assessed through the recording and reporting of medical device incidents.

In addition, any Adverse Event (AE) or Serious Adverse Event (SAE) related to the conduct of the study that would occur in a subject participating in the clinical trial will be recorded and reported through AE CRF. The analysis of these AEs/SAEs should be used to update the Forielle Risk Assessment as well as Instruction For Use.

Of note, given the design of this study and the reporting period for safety surveillance, assessment of serious adverse device effects in offspring of subjects participating in the clinical trial is not applicable (see Section 7.4.1).

7.4.1 Definition of the Safety Surveillance Reporting Period

The reporting period for overall safety surveillance begins when the subject is included in the clinical trial (date of first signature of informed consent) and continues through the Study Exit (PET Days 70-84/Weeks 10-12). Differences in the recording and assessment of AEs related to the conduct of the study and medical device incidents may be found in Sections 7.4.2.3 and 7.4.3.2, respectively. There is no pregnancy follow-up planned in the study. Hence, any abnormal pregnancy outcome and/or congenital anomaly/birth defect that would be reported to the Sponsor by the investigator will be collected, processed and followed-up by the Sponsor's Global Drug Safety Department as a spontaneous case report

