7.1.7 Post Embryo Transfer Days 70-84/Weeks 10-12 (Study Exit)

The study exit visit will occur 70 to 84 days (10 to 12 weeks) after embryo transfer. For subjects who are not pregnant at the PET Days 14 or PET Days 21-28 visits, the Days 70-84/Weeks 10-12 visit will be a telephone visit to record adverse events, device incidents, and concomitant medications. The investigator will ensure negative ultrasound results are entered for ultrasounds that were not performed due to the subject not being pregnant.

For subjects with an ongoing pregnancy at the PET Days 21-28 visit, the following assessments will occur at the visit PET Days 70-84/Weeks 10-12 visit:

- Confirm ongoing pregnancy via obstetric ultrasound (transvaginal or abdominal)
- Confirm the number of foetuses, confirm foetal vitality based on the presence of foetal heartbeat(s) and confirm the development of normal pregnancy (assessments to be made for each foetus present on ultrasound)
- Record adverse events, device incidents and concomitant medications

In the event a subject cannot return to the site for the PET Days 70-84 visit, ultrasound report confirming ongoing pregnancy details required (number of foetuses, confirmation of foetal vitality based on the presence of foetal heartbeat and confirmation of the development of normal pregnancy for each foetus present on ultrasound) may be provided to the investigator. In these cases, final study procedures may be performed via telephone and the investigator will enter ultrasound results from the report provided.

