7.4.2.2 Definition of Serious Adverse Events

Serious Adverse Events are defined as AEs that:

- a) Led to death
- b) Led to serious deterioration in the state of health of the subject, that either resulted in
 - a. A life-threatening illness or injury, or
 - b. A permanent impairment of a body structure or a body function, or
 - c. In-patient or prolonged hospitalization, or
 - d. Medical or surgical intervention to prevent life-threatening illness or injury or permanent impairment to a body structure or a body function
- c) Led to foetal distress, foetal death or a congenital abnormality or birth defect

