8.5.4 Analysis of Safety and Other Endpoints

Device incidents will be summarized using frequency and percentages for two treatment groups.

Clinical laboratory assessments (E₂ and P₄, etc.) will be presented in listings appropriately.

Substance Code Clinical Performance and Safety Investigation of ENDOmetrial Washing
MEdical DEvice Forielle
Protocol Number MS 700623_0009

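### Pregnancy loss before Study Exit has two conflicting safety routes, and no safety count of it by randomised arm is specified

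*Combined protocol and SAP*

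**What the plan says.** **Safety text.** Section 7.4.2.2(c) counts as serious any adverse event that "Led to foetal distress, foetal death or a congenital abnormality or birth defect". Section 7.4.2.3 puts adverse events on the AE form up to Study Exit, but only those related to study conduct. Section 7.4.1 sets a surveillance period that "continues through the Study Exit (PET Days 70-84/Weeks 10-12"). The same section then states: "There is no pregnancy follow-up planned in the study". It goes on to say that "any abnormal pregnancy outcome and/or congenital anomaly/birth defect that would be reported to the Sponsor by the investigator will be collected" and processed by the sponsor's "Global Drug Safety Department as a spontaneous case report". No date limits that sentence. Section 7.4 adds that "assessment of serious adverse device effects in offspring of subjects participating in the clinical trial is not applicable", and refers to the reporting period in 7.4.1.

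**Pregnancy data.** Section 7.1.6 records the number of sacs at PET Days 21-28. For women whose pregnancy is continuing, Section 7.1.7 has this instruction at exit: "Confirm the number of foetuses, confirm foetal vitality based on the presence of foetal heartbeat(s) and confirm the development of normal pregnancy". Ongoing pregnancy (yes/no) is a secondary endpoint (8.3.2), compared between arms by logistic regression (8.5.3).

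**Safety analysis.** Section 8.5.4 has one by-arm item: "Device incidents will be summarized using frequency and percentages for two treatment groups". Section 8.4 restricts the Safety set to randomised women in whom the wash was at least tried, and groups them by the procedure actually received.

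**The concern.** The wash is put into the cavity where the embryo will implant, and Section 3.1.2 says that the study should confirm clinical safety. Loss of a pregnancy after implantation is therefore a directly relevant harm. As written, a loss before exit is a serious adverse event under one section and a spontaneous report under another. The safety analysis does not count it in either arm.

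The route matters. Section 7.4.4 requires the sponsor to tell all other investigators within 24 hours of a serious adverse event related to study conduct; it states no such step for a spontaneous report. Section 7.4 also expects the analysis of adverse events to feed the risk assessment and the instructions for use, but Section 8.5.4 specifies no adverse event table. Investigators know the allocation (6.10), and they judge whether an event is related to study conduct. A count that depends on that judgement could differ between arms for reasons unrelated to the device.

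**Working it through.** The plan gives no figure for pregnancy loss, so there is none to reproduce. The only planning figure used below is the arm size: 916 / 0.85 = 1,077.6, rounded up to 1,078 per arm, and 2 × 1,078 = 2,156, as in Section 8.1.

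**1. Is the loss inside the surveillance period?** The scans fall at PET Days 21-28 and 70-84. The interval between them is 70 − 28 = 42 days at the shortest and 84 − 21 = 63 days at the longest. All of it lies before Study Exit, so a loss in this window is within the period defined in 7.4.1.

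**2. Follow one case through the text.** Take a woman with one sac at the first scan and no heartbeat at the second.
- Sections 7.4.2.2(c) and 7.4.2.3: a serious adverse event, entered on the AE form if the investigator judges it related to study conduct.
- Section 7.4.1: an abnormal pregnancy outcome, processed as a spontaneous case.
- Sections 8.3.2 and 8.5.3: *no* for ongoing pregnancy.

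The first two lines compete. The statement that no pregnancy follow-up is planned also cannot be literally true alongside Sections 7.1.6 and 7.1.7, unless it refers to the time after exit.

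**3. What does the ongoing pregnancy endpoint show?** Per woman:
- ongoing = P(sac) × [1 − P(loss given sac)]
- loss = P(sac) × P(loss given sac)

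Illustration per 100 women. All four rates are assumptions, not figures from the plan:
- First arm, 44 with a sac and 20% lost: ongoing 44 × 0.80 = 35.2; lost 44 × 0.20 = 8.8.
- Second arm, 39 with a sac and 10% lost: ongoing 39 × 0.90 = 35.1; lost 39 × 0.10 = 3.9.

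The ongoing rates are practically equal, while losses per 100 women differ by 8.8 − 3.9 = 4.9. Loss of one of two foetuses does not register at all in a yes/no endpoint, although it can be derived from the sac and foetus counts.

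**4. Who is in the safety comparison?** If every woman receives her allocated procedure, none of the 1,078 planned controls enters the Safety set. A control washed by mistake would enter it as a Forielle subject. Device incidents concern the device and its labelling, so they cannot arise in an unwashed woman. Section 8.5.4 does not name its analysis set; if it is the Safety set, the control column has no denominator.

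**5. Where does observation stop?** Retrieval is Day 2 after randomisation and transfer is Day 5 or Day 7, so transfer follows retrieval by 3 or 5 days. Counting retrieval as gestational day 14 (a convention assumed here), transfer is day 17 or 19. Exit then falls between 70 + 17 = 87 days (12 weeks 3 days) and 84 + 19 = 103 days (14 weeks 5 days). Most birth defects, which item (c) also lists, could not be seen by then.

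**The case against.** The best defence is that Section 7.4.1 means outcomes after exit. It first sets the period to Study Exit, then says that no pregnancy follow-up is planned, and presents the spontaneous route as the consequence. Since pregnancies are plainly followed to PET Days 70-84, that is a natural reading. It also describes how the sponsor processes reports and does not cancel the site's duty under 7.4.2.3. This is plausible and may well be the intention. But the sentence covers *any* abnormal outcome and gives no date, so the text needs a clarifying clause.

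A second defence is that details of tables are deferred to separate analysis plans (8.5.1), and that Section 7.4 foresees an analysis of adverse events. That stands as a caution: the point concerns what the available documents specify.

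Stronger readings that a reader might infer, and why they fail:
- *Losses inside the trial are not counted by arm.* They are, indirectly: each complete loss before exit is a *no* in an endpoint compared by arm, and subject-level loss can be derived from the scans.
- *Harm would be hidden.* Sacs are the numerator of the primary endpoint, so more sacs without more ongoing pregnancies would be visible to anyone who sets the two results side by side. What is missing is a planned count.
- *A stated number of losses would be misrouted.* The documents give neither the share of women with a sac nor a loss rate, and a loss judged unrelated to study conduct need not go on the AE form under either reading.
- *All effects on offspring are dismissed.* Section 7.4 limits its statement to serious adverse device effects.
- *Delivery outcome must be collected.* The protocol openly ends follow-up at exit and defines its safety objective through device incidents (4.2). Going further is a design preference.

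**Conclusion.** The point holds as an inconsistency in the safety text and a gap in the specified safety analysis. Sections 7.4.1 and 7.4.2.2(c) give different routes for a loss before Study Exit, and the post-exit reading that would reconcile them is not written down. Loss enters the arm comparison only within ongoing pregnancy, where it is combined with implantation. No safety count by arm is specified, and the Safety set provides no control denominator.

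The documents do not allow an estimate of how many events are affected. The comparison of 8.8 with 3.9 losses per 100 women shows only that equal ongoing rates can go with different loss; it rests on assumed rates. The primary and secondary comparisons themselves are not affected. The change is worth making because the data are already scheduled and it adds the missing control group to the safety comparison.

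**What to change.** 1. **Reconcile the safety text.** Amend Section 7.4.1, in agreement with 7.4, 7.4.2.2 and 7.4.2.3, so that the spontaneous route applies only to outcomes learned after Study Exit. Losses up to exit should be recorded on the trial CRF in the same way in both arms. Make clear that the absence of pregnancy follow-up refers to the time after exit.
2. **Add one table to Section 8.5.4.** Define pregnancy loss as a sac at PET Days 21-28 and no viable foetus at PET Days 70-84. Show it by randomised arm, with all randomised women as the main denominator and not the Safety set. Give women with a sac but no exit result their own row. Show the rate per woman with a sac as descriptive only: it conditions on a post-randomisation outcome that the device is meant to change.
3. **State the limit.** Say in the report that the safety conclusion ends at Study Exit.

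Cost: a few sentences of protocol text, consistent CRF instructions, one table from scans already scheduled, and one limiting sentence. No visit or procedure is added.

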7.4.2 Clinical Trial Adverse Events

AEs related to the conduct of the study will be recorded as described below.

Substance Code Clinical Performance and Safety Investigation of ENDOmetrial Washing
MEdical DEvice Forielle
Protocol Number MS 700623_0009

7.4.2.1 Definition of Adverse Event

An AE is defined as any untoward medical occurrence, unintended disease or injury, or untoward clinical signs (including abnormal laboratory findings) in subjects participating in a clinical trial. Incidents with the Forielle device will be reported as detailed in Section 7.4.3.

7.4.2.2 Definition of Serious Adverse Events

Serious Adverse Events are defined as AEs that:

- a) Led to death
- b) Led to serious deterioration in the state of health of the subject, that either resulted in
 - a. A life-threatening illness or injury, or
 - b. A permanent impairment of a body structure or a body function, or
 - c. In-patient or prolonged hospitalization, or
 - d. Medical or surgical intervention to prevent life-threatening illness or injury or permanent impairment to a body structure or a body function
- c) Led to foetal distress, foetal death or a congenital abnormality or birth defect

7.4.2.3 Method of Recording and Assessing Adverse Events

At each visit after enrolment, from Start of stimulation at Day -12 up to Study Exit (PET Days 70-84/PET Weeks 10-12) or final study contact, the subject will be queried on changes in her condition. During this reporting period of the study any AE related to the conduct of the study will be recorded and assessed on an AE case report form (CRF) (distinct from the Device Incident CRF) whether reported by the subject to the investigator or observed by the investigator.

The assessment by investigator shall include a description of the event, its duration (onset and resolution), dates its severity and seriousness, its relationship with the conduct of the Study, any other potential causal factors, any treatment given or other action taken (including withdrawal to the study) and its outcome.

7.4.3 Medical Device Incidents

Device Incidents will be reported as described below.

7.4.3.1 Definition of Medical Device Incident (MEDDEV 2.12-1, Rev. 8, adapted to definitions above)

A medical device incident is 'any malfunction or deterioration in the characteristics and/or clinical performance of a device, as well as any inadequacy in the labelling or the IFU which, directly or indirectly, might lead to or might have led to the death of a patient, or USER or of other persons or to a serious deterioration in their state of health'. A medical device incident that would require reporting include:

Substance Code Clinical Performance and Safety Investigation of **ENDO**metrial Washing
MEdicinal **DE**vice Forielle
Protocol Number MS 700623_0009

- a) Serious public health threat: Any event type which results in imminent risk of death, serious deterioration in state of health, or serious illness that requires prompt remedial action (MEDDEV 2.12-1 rev.8).
- b) Death or UNANTICIPATED serious deterioration in state of health of a subject that resulted in
 - 1) A life-threatening illness or injury, or
 - 2) A permanent impairment of a body structure or a body function, or
 - 3) In-patient or prolonged hospitalization, or
 - 4) Medical or surgical intervention to prevent life-threatening illness or injury or permanent impairment to a body structure or a body function
- c) Other events: events that have an established link between the device and the event

7.4.3.2 Method of Recording and Assessing Medical Device Incidents

At each visit from Day 2 PR up to Study Exit (PET Days 70-84/Weeks 10-12), the subject will be queried on medical device incident associated with the use of Forielle. During this reporting period any medical device incident will be recorded and assessed on the Device Incident CRF, whether reported by the subject to the investigator or observed by the investigator.

The assessment by the investigator shall include the determination of the seriousness of the incident and its relationship with the medical device.

7.4.4 Procedure for reporting Serious adverse events and/or Medical Device Incident

Investigator **MUST** Report all medical device incidents to the sponsor using Manufacturing Incident Report Form within 24 hours.

The sponsor shall:

- Inform within 24 hours all other investigators of medical device incident reports and SAE related to the conduct of the study
- Notify the manufacturer of all medical device incidents within 24 hours

The manufacturer shall:

- Conduct an investigation of the medical device incident and determine whether the risk analysis needs to be updated and whether corrective actions are required.
- Report all medical device incidents to the competent authority in accordance with the Meddev 2.12-1, Rev. 8 guidance.

Substance Code Clinical Performance and Safety Investigation of ENDOmetrial Washing
MEdical DEvice Forielle
Protocol Number MS 700623_0009

7.4.5 Monitoring of Subjects with Medical Device Incidents and/or Adverse Events related to the conduct of the study

Any medical device incident that would require reporting, as defined in Section 7.4.3.1, and AE related to the conduct of the study, must be monitored and followed up by the Investigator or Sub-Investigator until stabilization of the subject health's condition or until the outcome is known, unless the subject is documented as "lost to follow-up". Reasonable attempts to obtain this information must be made and documented.

It is also the responsibility of the Investigator or Sub-Investigator to ensure that any necessary additional therapeutic measures and follow-up procedures are performed. The Sponsor will actively follow-up and collect information on any SAEs related to the conduct of the study.

7.4.6 Clinical Laboratory Assessments

Serum samples will be collected for E₂ and P₄ at the HCG Triggering day to be analysed locally by the centre for the purposes of confirming eligibility criteria. Each site will collect an extra serum sample for P₄ evaluation to be carried out by the central laboratory (PPD) to validate local laboratory evaluation of P₄ retrospectively to validate subject inclusion in planned analyses.

8 Statistics

8.1 Sample Size

The main aim of the study is the evaluation of the clinical performance of Forielle in restoring favourable condition of endometrial milieu, after Controlled Ovarian Stimulation. For this purpose, clinical performance will be measured by assessing the difference in implantation rate in the treated arm compared to the control (standard clinical practice). Generally, the average implantation rate of ART is considered of about 25% (Nastri et al. 2013). Several works in the literature suggested the key role of endometrial receptivity on the ART outcomes (Evans et al. 2012). An improvement of about 6% in implantation rate from the usual ART outcome is clinically relevant difference. Thus, for the calculation of sample size, a clinically important difference of 6% was assumed and an interim clinical performance analysis assuming that 2 sequential tests are made using the O'Brien-Fleming spending function to determine the test boundaries. Sample sizes of 916 each arm achieve 80% power to detect a difference of 0,06 between the group proportions of 0,25 and 0,31 at a significance level (alpha) of 0,050 using a two-sided z-test with continuity correction and allocation ratio of 1:1. The total number of women to be randomised is 2,156, considering a drop-out rate of 15%.

| Target Power | Actual Power | N1 | N2 | N | P1 | P2 | Alpha |
|--------------|--------------|-----|-----|------|------|------|-------|
| 0.80 | 0.80025 | 916 | 916 | 1832 | 0.25 | 0.31 | 0.05 |

Substance Code Clinical Performance and Safety Investigation of **ENDO**metrial Washing
MEdical **DE**vice Forielle
Protocol Number MS 700623_0009

Details when Spending = O'Brien-Fleming, N1=916, N2=916, P1=0,25, P2=0,31, Continuity Correction.

| Look | Time | Lower Boundary | Upper Boundary | Nominal Alpha | Incremental Alpha | Total Alpha | Incremental Power | Total Power |
|------|------|----------------|----------------|---------------|-------------------|-------------|-------------------|-------------|
| 1 | 0.5 | -2.96259 | 2.96259 | 0.003 | 0.003 | 0.003 | 0.16425 | 0.164 |
| 2 | 1 | -1.96857 | 1.96857 | 0.049 | 0.047 | 0.047 | 0.63600 | 0.800 |

The required significance level for stopping the study for clinical performance is 0.003 to first look (50% of patients) and 0.049 at second look (final). The overall power is 80%.

8.2 Randomisation

Eligible subjects will be randomised to receive either the intervention (Forielle endometrial washing) or no endometrial washing following oocyte retrieval on Study Day 0, the HCG Triggering day, in a 1:1 ratio.

At the HCG triggering day, on study day 0 all eligible women subjects will be randomised in ratio of 1:1 to one of two parallel treatment groups:

- Forielle
- Control (No endometrial washing)

Women subjects will be stratified with respect two factors:

- Age (age <32; 32 ≤ age <38; 38 ≤ age ≤ 41)
- n° of follicles (>16mm) (5 ≤ n° follicles ≤ 9; 10 ≤ n° follicles ≤ 14)

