5.1 Overall Trial Design and Plan

This is a multicentre, prospective randomised controlled, interventional investigation to assess the safety and clinical performance of Forielle, a medical device for endometrial washing, in restoring favourable endometrial condition to implantation after COS during ART.

The study protocol consists in assessing the clinical performance of Forielle in restoring favourable condition of endometrial milieu after COS. Clinical Performance will be measured by comparing implantation rate in the treated arm compared to the control. The trial aims to enrol 2,156 women from at least six centres in Italy.

Infertile females aged ≤ 41 years with no more than one previous implantation failure will be assessed for eligibility for the trial after providing written informed consent. Subjects will under COS according to standard of care clinical practice. There is no limitation in the gonadotrophin stimulation protocols used; however, triggering must be done with HCG. Eligible subjects will be randomised to receive either the intervention (Forielle endometrial washing) or no endometrial washing following oocyte retrieval on Study Day 0, the HCG Triggering day, in a 1:1 ratio. Oocyte retrieval and endometrial washing (Forielle-treated group) will occur during the same surgical procedure. The entire ART cycle will be performed according to clinical practice of the centre based on each subject's clinical profile.

Retrieved oocytes will be fertilized per ICSI standard clinic practice and the embryology lab will calculate the fertilization rate for each subject. Beginning approximately 24 hours after ICSI, the embryology lab will evaluate embryo for quality daily, with the most viable embryos selected for implantation (Day 5 PR for embryos transferred in the cleavage stage and Day 7 PR for embryos transferred in the blastocyst stage).

Luteal support/endometrial preparation will be done with progesterone (100 mg intramuscular injection at the Oocyte Pick Up [OPU] day and 600 mg of vaginal progesterone from the day after OPU and administered daily). At the Embryo Transfer visit (Day 5 PR or Day 7 PR), a maximum of 2 fertilized embryos or blastocysts will be transferred; luteal support (daily administration of 600 mg of vaginal progesterone) will continue.

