6.3 Assignment to Treatment Groups

Subjects will be randomised in a 1:1 ratio to receive endometrial washing with Forielle or no endometrial washing (control group); randomised subjects will be stratified by age (< 32 years of age; 32 to 37 years of age; 38 to 41 years of age) and number of follicles >16 mm (5 to 9 follicles >16 mm; 10 to 14 follicles >16 mm). Although the subject and the investigator and site staff will be aware of the endometrial washing condition, the embryology lab will be blinded to the randomisation procedure and will not know the endometrial washing condition.

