8.5.2 Analysis of Primary Endpoints

The primary endpoint subject implantation rate is defined as number of intrauterine gestational sacs divided by the number of embryos transferred, as assessed at PET Days 21 to 28.

Mean subject implantation rate as assessed at PET Days 21-28 in subjects treated with Forielle endometrial washing procedure will be compared to the mean subject implantation rate in subjects who receive no endometrial washing (control group) following COS.

For the primary endpoint analysis addition to summary statistics, differences in mean subject implantation rate between study procedure and control procedure will be investigated and compared using Gamma/log normal regression model. The analysis model will include treatment procedure as the fixed effect and Embryo Transfer Day (Day 5 PR or Day 7 PR), age, number of follicles at baseline and number of embryos transferred per subject as covariates.

To evaluate the treatment comparison, estimated mean differences will be presented together with two-sided 95% confidence intervals and p-values. Appropriate distribution will be decided based on good ness of fit (residual sum of squares) value.

This primary endpoint analysis will be tested by planned group sequential design with O'Brien-Fleming type spending function. The study for clinical performance will be stopped at significance level of 0.003 in first (50% of subjects) interim analysis and at significance level 0.049 in final analysis.

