8.5.3 Analysis of Secondary Endpoints

For the secondary endpoints, subject pregnancy result (positive/negative) and subject with confirmed pregnancy (yes/no), the pregnancy rate at PET Day 14 and ongoing pregnancy rate at PET Days 70-84 will be estimated and compared using logistic regression model including Embryo Transfer Day (Day 5 PR or Day 7 PR), age and number of follicles at baseline as covariates. Estimates of odds ratio, confidence intervals and relevant p-values will be presented for each endpoint.

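### The primary and logistic models have no term for centre, although each centre runs the ART cycle by its own practice; the comparison stays valid but gives up a little precision

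*Combined protocol and SAP*

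**What the plan says.** **Allocation.** Section 8.2 states: "Women subjects will be stratified with respect two factors". The two are age (three levels) and number of follicles above 16 mm (two levels). Section 6.3 gives the same pair: "randomised subjects will be stratified by age" and follicle count. Neither section says whether the lists are central or kept by centre.

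**Primary model.** In section 8.5.2 and the synopsis, "The analysis model will include treatment procedure as the fixed effect". The other terms are transfer day and "age, number of follicles at baseline and number of embryos transferred per subject as covariates".

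**Secondary models.** Section 8.5.3 uses logistic regression with transfer day, "age and number of follicles at baseline as covariates".

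Centre is in none of these lists. No random centre effect, by-centre summary or treatment-by-centre check is described.

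**Local practice.** Section 5.1 says: "The entire ART cycle will be performed according to clinical practice of the centre". It also says: "There is no limitation in the gonadotrophin stimulation protocols used". Section 2 plans at least six Italian sites, mixing public, publicly authorised private and private centres. Section 8.5.1 defers further detail to separate interim and final SAPs, whose text is not in the document reviewed.

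**The concern.** Success rates can be expected to vary between clinics that choose their own stimulation protocol, laboratory routine and transfer policy. Age and follicle count describe the woman and do not capture how a clinic or its laboratory works. Centre is known for every woman before randomisation and cannot be altered by treatment, so it is a natural adjustment variable.

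Leaving it out has two consequences. Between-centre variation that the existing covariates do not explain stays in the residual. And if the arms happen to be unevenly split within good or poor centres, nothing in the analysis corrects for it. What is at stake is the width of the confidence interval and a little power.

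**Working it through.** **Inputs from section 8.1.** Rates 0.25 and 0.31; two-sided alpha 0.05; continuity correction; two looks with bounds 2.96259 and 1.96857; 916 per arm; 15% drop-out.

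**Assumed.** The between-centre variance, because the documents give none. It is expressed as an intraclass correlation (ICC), the share of the binary outcome variance that lies between centres.

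**1. The plan's own figure.**
- Standardised effect = (0.06 − 1/916) / √(2 × 0.28 × 0.72 / 916) = 0.0589 / 0.02098 = 2.81.
- The two-look normal calculation with the stated bounds gives power 0.8003 (stated 0.80025), first-look power 0.1642 (stated 0.16425) and overall alpha 0.0500.
- 1,832 / 0.85 = 2,155.3, rounded up to 2,156.

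The sample size reproduces. It contains no allowance for centre and needs none to be valid.

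**2. What a centre term would add.** With unpooled variance the starting power is 80.2%. A centre term that removes all between-centre variance multiplies the residual variance by (1 − ICC), so the standardised effect is divided by √(1 − ICC), and the same power needs 916 × (1 − ICC) women per arm. The SD of centre rates is √(ICC × 0.28 × 0.72).

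| ICC (assumed) | SD of centre rates, points | Power with centre | Equivalent n per arm | Women, both arms |
|---|---|---|---|---|
| 0 | 0 | 80.2% | 916 | 0 |
| 0.005 | 3.2 | 80.4% | 912 | 8 |
| 0.01 | 4.5 | 80.6% | 907 | 18 |
| 0.02 | 6.3 | 81.0% | 898 | 36 |
| 0.05 | 10.0 | 82.2% | 871 | 90 |
| 0.10 (outer case) | 14.2 | 84.2% | 825 | 182 |

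These are upper values for each ICC, because they credit nothing to covariates already in the model.

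**3. Chance imbalance.** If allocation ignores centre, the treatment difference shifts by chance with SD of about (SD of centre rates) × 2/√1,832. That is 4.49 × 0.0467 = 0.21 points at ICC 0.01 and 10.04 × 0.0467 = 0.47 points at ICC 0.05. The target difference is 6 points and the standard error of the difference is about 2.1 points.

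**4. Simulation check.** A binary outcome was simulated 20,000 times per setting, comparing the unadjusted z-test with a centre-stratified Cochran-Mantel-Haenszel test at the final bound. With allocation not balanced by centre, the type I error of the unadjusted test lay between 0.047 and 0.053 for 6, 12 and 30 centres and ICC from 0 to 0.10. Power, unadjusted / adjusted:

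| Centres | ICC 0 | ICC 0.01 | ICC 0.05 |
|---|---|---|---|
| 6 | 81.5 / 81.3% | 81.4 / 81.7% | 81.3 / 83.0% |
| 12 | 81.0 / 80.9% | 81.2 / 81.4% | 81.3 / 83.1% |
| 30 | 81.3 / 80.8% | 82.0 / 81.7% | 81.6 / 82.8% |

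Read the gains rather than the levels: the levels are in line with the 81.5% that the two-look calculation gives without continuity correction. With 30 centres and little centre variation, the adjusted test was slightly worse.

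**5. If allocation were in fact balanced by centre.** Omitting centre would then make the test conservative: type I error 0.046 at ICC 0.01 and 0.043 at ICC 0.05, against 0.047 and 0.049 with centre adjusted for.

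**The case against.** The strongest reply is that this is a choice about precision in a sound design. Women are randomised individually, so the unadjusted comparison is unbiased, and its interval already carries the uncertainty from centre imbalance. That stands.

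Much of the local variation is also already dealt with. Number of embryos and transfer day are in the primary model. The protocol itself fixes ICSI, the HCG trigger, a maximum of two embryos and the luteal support, and it restricts eligibility by BMI, ovarian reserve and hormone levels. This stands in part: it reduces what a centre term can recover, by an amount the documents do not let one calculate. Transfer day and number of embryos are settled after randomisation, which is a separate matter. Laboratory and clinic effects beyond them remain.

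The variance argument does not carry straight over to the logistic models. There, a centre term changes the odds ratio to one conditional on centre and generally widens its standard error, even where power rises slightly. This stands and shapes the fix. The planned Gamma or log-normal model was not simulated either.

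The separate SAPs may add centre. That is possible, but the protocol's explicit covariate lists do not.

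A reader might infer that the stratification in section 8.2 is defective. The documents do not support that: two patient-level factors are a legitimate choice, and the gain sought here comes from the model.

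**Conclusion.** The point holds as a minor improvement. Both covariate lists omit centre in a trial that leaves the ART cycle to local practice. For an ICC of 0.01 to 0.05 the loss is about 0.4 to 2 power points, or about 18 to 90 of 1,832 women. This rests on an assumed ICC, on the binary variance of section 8.1 rather than the variance of the sacs-per-embryo ratio, and on existing covariates absorbing none of the centre variation; if they absorb some, the gain is smaller.

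Three stronger readings are tempting and are not supported:

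- **Bias or inflated type I error.** Individual randomisation rules out the first. The simulated error stays near 0.05, or falls below it if allocation is balanced by centre.
- **A sample size that is too small.** The stated 916 per arm and 2,156 in total both reproduce.
- **A markedly larger gain.** A figure near 130 women would need a 10-point SD of centre rates together with a residual variance of about 0.14 (0.01 / 0.14 = 7.1% of 1,832), and the documents give no such variance.

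**What to change.** Add centre as a categorical term to the primary model in 8.5.2 and to the logistic models in 8.5.3, and label the resulting odds ratios as conditional on centre. Fix a rule for pooling small centres before the interim, and apply the same model and rule at interim and final. Leave randomisation unchanged.

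**Cost.** The covariates are listed in the protocol, so this changes the synopsis, 8.5.2 and 8.5.3 as well as both SAPs, under the amendment procedure in 10.6. Six is a minimum number of sites: 1,832 / 6 is about 305 evaluable women per centre, but 30 centres would leave about 61, and the simulation shows a slight loss there when centre variation is small. The pooling rule matters most if many small centres join. No extra data are needed.
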